9.2 Inclusion Criteria

1. For females and males 18 years old or older: females should be on adequate contraception if they are of child-bearing potential, which should be documented by a clinician, unless patients or their spouse/partner(s) have previously undergone a sterilization procedure. Adequate contraception will be considered:
 - Intrauterine device (IUD),
 - Hormone implants,
 - Injectable contraceptives,
 - Oral contraceptives plus a barrier method (male condom, female condom or diaphragm),
 - Abstinence, or
 - A vasectomized partner.
2. Meet revised ACR criteria and 2012 SLICC criteria for SLE and have: a) a baseline SLEDAI-2K ≥ 4 and <20 or a clinical SLEDAI-2K ≥ 2 (not considering anti-dsDNA or complement levels) and b) lack of BILAG A flare at baseline (See Appendix 3).
3. Stable doses of immunosuppressants and/or antimalarials for at least 3 months, and/or corticosteroids for at least 2 weeks. The prednisone dose may be increased after screening visit as long as the total dose is less than 20 mg of prednisone or equivalent per day and the subject is on stable dose for at least 2 weeks prior to their Day 1 visit. If on statins, should have been on stable doses for at least 6 months.
4. Allowed concomitant lupus-related medications
Antimalarials,
Prednisone ≤ 20 mg daily or equivalent doses of other corticosteroids;
Immunosuppressants:

Mycophenolate mofetil, up to 3000 mg/day,

Methotrexate, up to 30 mg/week,

Azathioprine, up to 3 mg/kg/day,

Leflunomide, up to 20 mg/day,

Cyclosporine, up to 5 mg/kg/day

Tacrolimus, up to 0.1 mg/kg/day

NSAIDs and aspirin

Note: While it would be highly desirable to maintain corticosteroid dosage at constant level for trial duration, it is impractical to anticipate that all patients with active SLE can be maintained without therapy modification for an 8-month period. Because corticosteroids are acceptable agents for treatment of the vast majority of minor lupus flares, and patients with major flares (BILAG 2004 A or recent change in medications) will be excluded, this will provide standardized treatment across study population that can be easily analyzed. An increase in prednisone dose of less than or equal to 10 mg/day from their prednisone dose at study entry will be permitted during the trial for increased disease activity with a standardized taper allowable in small monthly decrements to the patient's baseline dose or 5 mg/day, whichever is less.

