9.4 Screening and Randomization

Subjects will review and sign informed consent document, and medical history, physical exam, disease activity (SLEDAI-2K), screening labs and echocardiogram will be performed.

Echocardiogram will not be performed if patient is rescreened within 6 months and previous result is normal or if patient had normal Echocardiogram within 6 months prior to screening.

Routine laboratory data obtained within 30 days of the screening visit under the natural history protocol 94-AR-0066 can be used for screening. Screening labs will include infectious disease testing for HIV, Hepatitis B, Hepatitis C and Tuberculosis if they have not been obtained within the last 6 months. As mentioned above, postmenopausal women without a DEXA scan in the last year will undergo a DEXA scan to assess eligibility. The window between screening and baseline must be less than 46 days, otherwise subjects will need to be rescreened regarding labs. Inclusion/Exclusion Criteria will be signed off based on screening labs and assessment. Patients who meet these criteria will be randomized to a sequence of active drug followed by placebo, or placebo followed by active drug in a 1:1 allocation ratio. Randomization and drug/placebo allocation will be done by the NIH clinical center research pharmacy after screening visit.

We will test Urinalysis (includes microscopic) on Screening and Month 8 visits on all patients. If patients have evidence of microscopic hematuria > 20 RBCs/uL(excluding normal menstruation cycle) it will be repeated twice at one month (+/- 7 days) intervals and if RBCs

are consistently more than 20 RBCs/uL then Urology consult will be placed. The following algorithm will be put in place, per recommendations by the Urology service at NCI:

1. Question patient about macroscopic hematuria > 20 RBCs/uL times 3 results.
 - a. If YES → Urology consult → Cytology
 - i. If abnormal cytology → Cystoscopy → FISH @ Mayo Labs for genetic changes for bladder cancer detection
 - ii. If normal cytology → Nothing

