11 DATA ANALYSIS

The study measures the primary and secondary outcome variables at 4 time periods in each subject. We will begin with a univariate investigation of the outcomes to check for outliers and distributional properties followed by an assessment for carryover effects. The analysis of the study will be conducted using a 2-period cross-over model by comparing matched pair differences for the subjects in the first sequence with those in the second sequence. We expect this analysis will indicate no difference between the groups. If we find no carry over effect the modeling will continue without controlling for sequence. If we do find a sequence effect we will account for it in our models. The analysis will be based on a repeated measures analysis accounting for treatment and period effects and incorporating the two baseline measures. We will use a generalized linear model and a Generalized Estimating Equations (GEE) framework with two dummy variables, one indicating treatment condition and the other indicating the baseline condition (the omitted or the reference condition is Placebo). We will use an unstructured covariance matrix and robust standard errors. The primary parameter of interest is the regression coefficient for the treatment condition (a contrast between the placebo and pioglitazone). This approach is attractive because it can handle non-normal and categorical outcomes. The analysis is robust to model mis-specification¹⁵⁴.

The approach used in testing the hypothesis under the three specific aims will be similar. For Specific Aim 1, we will perform a separate analysis for each outcome variable: CAVI/Sphygmocor, PAT and FDG/CT. We will also perform secondary analysis using serum and cellular CV biomarkers. Our first analysis will be a randomization based analysis with no

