covariates other than treatment and period effects. There are several confounding variables, especially medications that could contribute towards the variation in the outcome. We will expand the regression models by including them as predictors. If the number of confounding variables is large, we will use investigate a propensity score matching analysis. For Specific Aim 2, we will define a dichotomous clinical endpoint measuring lupus disease activity. Patients achieving an improvement of the SLEDAI-2K by 20%, a significant improvement in PGA and the absence of a BILAG 2004 A or B flare will be considered to have improved. Others will be defined as not having improved. The analysis for this score will be similar to the one proposed for Specific Aim 1. A GEE model will be used to assess treatment differences. We will also investigate the separate effects of each of these measures. The same approach used in Aim 1 will be taken for confounding variables using regression or propensity score adjustment. We will begin the investigation of Aim 3, assessment of innate and adaptive immune abnormalities in SLE, with a graphical analysis of the variables. We use multivariate methods to determine good summary measures of the various factors and compare the two treatments using the same models as defined for Aims 1 and 2.

Our primary analysis will be performed as an intent-to-treat analysis. If the subjects providing complete data are systematically different from those who dropped out, then the estimates based only on completers will be biased. We will investigate adjusting for differences in the populations who are completers and noncompleters and will consider multiple imputation to impute the missing values. Before the database is locked and final analysis performed, violations will be assessed on a case-by-case basis by the PI to determine if the medication change was such that it would adversely affect the study results. If changes may adversely affect data interpretation, subjects will be dropped from final analysis. A post hoc analysis of disease activity, measured by SLEDAI-2K, will be adjusted for burst steroids in excess of that permitted by the protocol. Analysis of prednisone doses, daily and cumulative will also be included.

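### The plan adjusts a randomised crossover contrast for unspecified medications and considers propensity-score matching; neither is needed, and medication changed during the trial is not excluded as a covariate

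*Combined protocol and SAP*

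**What the plan says.** Section 9.4 randomises patients to a treatment sequence "in a 1:1 allocation ratio". Section 11 bases the comparison on a two-period crossover model, "comparing matched pair differences for the subjects in the first sequence with those in the second sequence", fitted by GEE with an unstructured covariance matrix and robust standard errors.

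For Aim 1 the opening step is sound: it rests on the randomisation and admits no "covariates other than treatment and period effects". The plan then says that several variables, medications above all, confound the outcome, and continues: "We will expand the regression models by including them as predictors". If there are many of them, "we will use investigate a propensity score matching analysis". For Aim 2: "The same approach used in Aim 1 will be taken for confounding variables using regression or propensity score adjustment".

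The section does not list the variables, say when they are measured, define a large number of them, or state the unit of matching. It calls the unadjusted model the first analysis. The word primary is attached to the treatment coefficient and to intent-to-treat, not to any one model.

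Medication can change during the trial. The note in section 9.2 states: "An increase in prednisone dose of less than or equal to 10 mg/day from their prednisone dose at study entry will be permitted". It ties such an increase to a worsening of lupus activity while the patient is on study. Section 10.1 expects that outside providers may adjust or add immunosuppressants. Section 11 itself adjusts a post hoc SLEDAI-2K analysis for steroid bursts beyond the permitted amount, and separately plans an analysis of daily and cumulative prednisone dose.

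**The concern.** A confounder must be associated with treatment. Here every patient who completes receives both treatments in an order set by chance, so the probability of active drug in any period is one half by design. A medication that is constant across a patient's two periods cannot confound a comparison within that patient. A propensity score therefore has nothing to correct in the treatment contrast.

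Medication that differs between a patient's two periods is a different matter. It changed after randomisation, and under section 9.2 a prednisone increase is a response to disease activity, which pioglitazone is hypothesised to lower (Hypothesis 3). Adjusting for it conditions on a possible consequence of treatment.

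Two things are at stake. An adjusted estimate may answer a different question from the one the trial asks, and appear to conflict with the valid estimate, while the plan does not say which one decides. Matching may also give up some of the within-patient precision for which a crossover was chosen.

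**Working it through.** The plan gives no figure for the adjusted or matched analyses. Section 11.1 states no effect size, SD, within-patient correlation, alpha or power, so there is nothing to reproduce. From the documents come the 1:1 sequence randomisation, the within-patient contrast and up to 75 completers (section 8). Every other input below is an assumption.

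**1. Upper bound if pairing is lost entirely.** With within-patient correlation ρ, the variance of the paired mean difference is proportional to 2(1−ρ)/n and that of an unpaired one to 2/n. The SE ratio is 1/√(1−ρ):
- ρ = 0.5: 1.41
- ρ = 0.6: 1.58
- ρ = 0.8: 2.24

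At two-sided 0.05 and 80% power with n = 75 and ρ = 0.6, the detectable effect is 2.80 × √(0.8/75) = 0.29 SD paired and 2.80 × √(2/75) = 0.46 SD unpaired.

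**2. What matching would more plausibly do.** Active periods were matched to placebo periods across patients by caliper matching on a propensity score. Inputs: 76 patients, direct drug effect −0.30 SD, an on-trial medication used in 40% of placebo and 20% of active periods, and a medication coefficient of +0.5 SD. About 61 of the 76 active periods found a match, and only about 24 of those were the patient's own placebo period. The estimate moved from about −0.40 (the total effect) to about −0.30. Variance relative to the paired analysis was 1.31, 1.45 and 1.94 at ρ = 0.5, 0.6 and 0.8. The SE ratios are the square roots: 1.14, 1.20 and 1.39. At ρ = 0.6 the detectable effect becomes 0.29 × 1.20 = 0.35 SD, not 0.46.

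**3. Regression on an on-trial medication.** Let the medication be used in proportions p1 (active) and p0 (placebo), with coefficient b on the outcome. Then total effect = direct effect + b × (p1 − p0), and adjustment returns the direct part only. With direct effect −0.30, p0 = 0.40 and p1 = 0.20:
- b = +0.5: total = −0.30 + 0.5 × (−0.20) = −0.40; adjusted −0.30; 25% lost.
- b = −0.5 (the medication improves the outcome): total = −0.30 + (−0.5) × (−0.20) = −0.20; adjusted −0.30; the effect is enlarged by half.
- p1 = p0: total and adjusted agree; nothing is lost.

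In crossover simulations (76 patients, ρ = 0.6) the loss was 25% for b = +0.5. It rose to 50% when a common activity factor drove both medication and outcome. The largest loss was 67%, with that factor and use of 40% versus 10%. The unadjusted paired contrast recovered the total effect in every scenario.

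**4. Steroid increase triggered by activity.** Assume prednisone is raised whenever activity exceeds the placebo 70th percentile (30% of placebo periods), with a true drug effect of 0.3 to 0.5 SD and ρ = 0.6:
- The trigger is the outcome measurement itself and the steroid has no effect: 31–34% lost.
- Within-period correlation between trigger and final outcome is 0.5 and the steroid lowers activity by 0.3 to 0.5 SD: about 1–9% lost.
- That correlation is 0.3 and the steroid effect is 0.5 SD: the estimate is enlarged by 6–7%.

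The simulations used within-patient differences of a continuous outcome, not the full GEE with four time points. The percentages do not carry over directly to the dichotomous Aim 2 endpoint.

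**The case against.** The best defence is that section 11 never says the medications are on-trial ones. Its wording fits prognostic covariates at entry, where section 9.2 requires stable doses, and adjusting for those would remove no drug effect. On-trial changes have provisions of their own: case-by-case review, the post hoc steroid-burst analysis and the prednisone-dose analysis. The unadjusted model comes first, adjustment is an expansion of it, and matching for Aim 1 is conditional and only to be investigated.

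Much of this stands, and it rules out several stronger readings:

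- A reader might infer that the plan commits to adjusting for on-trial medication. It does so explicitly only for steroid bursts in a post hoc analysis. In the main models it leaves the matter open.
- A reader might infer that every adjusted analysis discards the pairing. Covariates inside the GEE leave the within-patient correlation in place. Only matching threatens it, and only if periods are matched across patients.
- A reader might infer that adjustment must understate benefit. Steps 3 and 4 show either direction. For the vascular endpoints the direction is less clear still, since section 6.4 describes corticosteroids as having mixed cardiovascular effects.
- A reader might take the move from 0.29 to 0.46 SD as the expected loss. It is the worst case.

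What the defence does not answer is that regression adjustment is stated as something that will be done, that nothing confines it to pre-randomisation values, and that no rule says which result prevails. Nor does it give a propensity score any purpose here. Differences between completers and non-completers are a separate problem, which section 11 addresses separately.

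**Conclusion.** The point holds as a defect of specification and of method choice, not as a finding that the first analysis is invalid. That propensity methods have no role in the randomised treatment contrast follows from the design and needs no assumption. That adjustment could capture part of the drug effect is conditional: it requires that on-trial medication enters the models and that its use differs by treatment. Sections 9.2 and 10.1 make this possible, and section 11 does not prevent it.

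Under the assumed scenarios the change in the estimate ranges from none to a loss of about two thirds, often toward zero, with enlargement possible when the added medication strongly improves the outcome. Precision loss applies to matching only: an SE ratio of about 1.14 to 1.39 at correlations of 0.5 to 0.8, bounded above by 1/√(1−ρ). The mechanism is most direct for disease activity, a secondary endpoint. The documents supply none of the inputs needed to narrow these ranges.

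**What to change.** In section 11:

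1. Name the treatment-plus-period crossover contrast, without further covariates, as the primary analysis for each endpoint.
2. Delete propensity-score matching (Aim 1) and propensity-score adjustment of the treatment contrast (Aim 2).
3. Limit covariates in the expanded models to a pre-specified list measured before randomisation, and label those models sensitivity analyses.
4. Use the month-5 value only through the planned crossover model with both baselines. It follows period-1 treatment, so it must not be listed as a pre-randomisation covariate.
5. Report on-trial medication changes by treatment period, as outcomes or as intercurrent events with a stated strategy, not as regressors. The prednisone-dose analysis already planned supplies part of this.

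The cost is wording only, with no added patients, visits or measurements. The one thing given up is an exploratory analysis.

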8 STUDY DESIGN AND METHODS

This will be a single-center, randomized, double-blind, placebo-controlled, crossover, proof-of-concept treatment trial enrolling 100 SLE patients including replacements due to screen failures and withdrawals. If a patient drops out of the study before completion both arms, another patient may be enrolled so that up to 75 patients complete the study. They will be treated for 3 months with 45 mg daily pioglitazone or placebo, undergo an 8 week washout period, then undergo crossover to the other arm for 3 additional months. Throughout the study, functional, anatomical and blood biomarkers of vascular damage, atherosclerosis risk and SLE activity will be collected. Pioglitazone has been chosen over rosiglitazone because it appears to have a significantly better safety profile regarding CV effects and lipid profile alterations⁹³, based on our experience in the rheumatoid arthritis (RA) trial⁵ and the small pilot study published by

another group that showed improvement in some metabolic parameters in SLE⁹², as well as our preliminary data which indicate improvement of vasculogenesis by pioglitazone but not rosiglitazone⁹⁴ in human SLE. We also have significant experience using this drug due to the recently completed clinical trial in RA³. The dose and study time period have been selected based on pioglitazone's macrovascular protective effects⁷⁴ and to allow detection of meaningful changes in endothelial function and disease activity, respectively. This is also based on the dose and study time period used in the RA trial, which showed significant effects on arterial stiffness, metabolic parameters, inflammatory markers and RA disease activity⁵.

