b) Lack of A or B flares on BILAG 2004: The BILAG 2004 assesses SLE activity based upon the premise of “intention to treat”^{129,130}. It has been widely used and is well validated (sensitivity 87%, specificity 99%, and positive predictive value of at least 80%). Within each organ/system, a combination of answers provides an activity score from A (very active) to E (not or never active) (see Appendix 3). Recent trials have modified BILAG 2004’s use to only the presence or absence of an A or B flare during the observation period as an outcome measure, thus incorporating BILAG’s sensitivity to flares in individual organ systems with the SLEDAI-2K. For the proposed study, the clinical disease activity endpoints will be patients achieving SLEDAI-2K improvement + absence of a BILAG 2004 A or B flare +improvement in PGA (see Appendix 3 and 7). There are eight systems: general, mucocutaneous, neurological, musculoskeletal, cardiorespiratory, vasculitis, renal and hematological. A score is calculated for each system depending on the clinical features present and whether they are new, worse, the same or improving in the last 4 weeks compared with previously. The most severe features in each system, which are deemed to require high dose steroids (prednisolone >20 mg daily or equivalent) and/or cytotoxic agents, characterize an A score. One or more features may have to be present to score an A, depending on the system. More moderate disease

items that would be considered appropriate to treat with lower dose steroids, antimalarials or non-steroidal anti-inflammatory drugs (NSAIDs) contribute to a B score. Mild symptomatic features that require just symptomatic therapy, for example with analgesics and NSAIDs, can only contribute to a C score. If there are no current symptoms but the system has previously been involved then a D is recorded. If the system has never been involved, it is scored E

c) *Health Related Quality of Life Questionnaire (HRQOL) (SF-36) and physician global assessment (PGA)*: This is a widely used tool to assess HRQOL with prior successful application in SLE^{131,132}. SF-36 assesses physical wellness, social and emotional well being and overall sense of mental health¹³¹. Completion takes 5-15 minutes (see Appendix 5).

d) Other: At each visit, C3, C4, anti-dsDNA, CRP and sedimentation rate will be quantified.

8.1.3 ***Specific Aim 3: Assess the immunoregulatory role of pioglitazone in lymphoid and myeloid cell subsets in SLE***

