Medical History, Physical Exam including vital signs, SLEDAI-2K	X							
Presenting Symptoms-Abbreviated Medical History		X	X	X	X	X	X	X
Physical Exam including vital signs		X	X	X	X	X	X	X
BILAG 2004, SLEDAI-2K ,PGA, SF36		X		X	X		X	
Blood Draw: insulin, glucose, lipids, EPCs, C3, C4, autoAbs, piHDL, cytokines, CRP, ESR , Aim 3 labs, Acute care panel, Lymphocyte Phenotyping TBNK, lipoprotein profile, Urinalysis (includes microscopic), p/c ratio.		X		X	X		X	X
Blood Draw: safety labs (CBC, LFTS, pregnancy tests in women of childbearing potential)		X	X	X	X	X	X	X
Screening labs and imaging. Blood draw: (pregnancy test, lipids, glucose, LFTs, CBC, Anti-ds-DNA, C3, C4, Urinalysis (includes microscopic), p/c ratio, Infectious disease	X							

testing), Echocardiogram (if it has not been obtained within the last 6 months) and DEXA scan (postmenopausal women without DEXA scan in the last year)								
Vascular function Studies		X		X	X		X	
Dispense Drug		X			X			
AE Review			X	X	X	X	X	X
Drug Accountability				X			X	
Health lifestyle Counseling (PRN)		X		X	X		X	
Urine analysis	X						X	X
PET-CT (subset of patients)		X		X				

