2	_____	Mucosal ulcers	Oral or nasal ulcerations.
2	_____	Pleurisy	Pleuritic chest pain with pleural rub or effusion, or pleural thickening.
2	_____	Pericarditis	Pericardial pain with at least 1 of the following: rub, effusion, or electrocardiogram or echocardiogram confirmation.
P			
2	_____	Low complement	Decrease in CH50, C3, or C4 below the lower limit of normal for testing laboratory
2	_____	Increased DNA binding	Increased DNA binding by Farr assay above normal range for testing laboratory.
1	_____	Fever	>38° C. Exclude infectious cause.
1	_____	Thrombocytopenia	<100,000 platelets / x10 ⁹ /L, exclude drug causes.
1	_____	Leukopenia	< 3,000 white blood cells / x10 ⁹ /L, exclude drug causes.

TOTAL SCORE: _____

3. BILAG SCORE.

BILAG 2004: The scoring system for the BILAG index of disease activity is based upon the principle of the physician's intention to treat. There are eight systems: general, mucocutaneous, neurological, musculoskeletal, cardiorespiratory, vasculitis, renal and haematological. A score is calculated for each system depending on the clinical features present and whether they are new, worse, the same or improving in the last 4 weeks compared with previously. The most severe features in each system, which are deemed to require high dose steroids (prednisolone >20 mg daily or equivalent) and/or cytotoxic agents, characterize an A score. One or more features may have to be present to score an A, depending on the system. More moderate disease items that would be considered appropriate to treat with lower dose steroids, antimalarials or non-steroidal anti-inflammatory drugs (NSAIDs) contribute to a B score. Mild symptomatic features that require just symptomatic therapy, for example with analgesics and NSAIDs, can only contribute to a C score. If there are no current symptoms but the system has previously been involved then a D is recorded. If the system has never been involved, it is scored E.

BILAG-2004 INDEX

Centre:

Date:

Initials/Hosp No:

◆ Only record manifestations/items due to SLE Disease Activity◆ Assessment refers to manifestations occurring in the last 4 weeks (compared with the previous 4 weeks)◆ **TO BE USED WITH THE GLOSSARY**

Record: ND Not Done

0 Not present

1 Improving

2 Same

3 Worse

4 New

Yes/No OR Value (where indicated)

*Y/N Confirm this is due to SLE activity (Yes/No)**CONSTITUTIONAL**

1. Pyrexia - documented > 37.5°C ()
 2. Weight loss - unintentional > 5% ()
 3. Lymphadenopathy/splenomegaly ()

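### The Aim 2 flare criterion sees only about the last 4 of 13 weeks of each treatment period and has no rescue rule, so an early flare that settles on permitted prednisone can be scored as improvement

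*Combined protocol and SAP*

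**What the plan says.** The Aim 2 endpoint in section 11 is dichotomous. Improvement means "Patients achieving an improvement of the SLEDAI-2K by 20%, a significant improvement in PGA and the absence of a BILAG 2004 A or B flare". For everyone else: "Others will be defined as not having improved". The definition gives no time window for the flare criterion and no rule for steroid rescue.

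Section 8.1.2 introduces the flare criterion by noting that recent trials use "the presence or absence of an A or B flare during the observation period as an outcome measure". Its sentence on this study asks only for absence of an A or B flare.

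In Table 3 the row "BILAG 2004, SLEDAI-2K ,PGA, SF36" is marked at baseline and months 3, 5 and 8. It is blank at months 1 and 6 and at unscheduled visits. Months 1 and 6 are safety visits that may be replaced by a local blood draw and a telephone call (section 9.5.2). Section 9.5.4 names flare as a reason for an unscheduled visit but requires no activity index there. The BILAG form in Appendix 3 states: "Assessment refers to manifestations occurring in the last 4 weeks (compared with the previous 4 weeks".

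On treatment changes, the note in section 9.2 says "An increase in prednisone dose of less than or equal to 10 mg/day from their prednisone dose at study entry will be permitted" for increased disease activity, with a taper in monthly steps. Section 10.1 stops study agent for flares that do not respond to the allowed treatment or that need disallowed therapy. Patients whose flares respond stay on. The steroid-adjusted analysis in section 11 reads: "A post hoc analysis of disease activity, measured by SLEDAI-2K, will be adjusted for burst steroids in excess of that permitted by the protocol".

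**The concern.** Hypothesis 3 is that disease activity falls on pioglitazone compared with placebo. A flare during treatment that needs extra prednisone is evidence against control on the assigned treatment, and the no-flare criterion appears to be there to record it. With BILAG scored only at the end of each period, a flare that has settled by then leaves no trace in that criterion. The prednisone that settled it, which may still be above the starting dose during a monthly taper, can also help the patient meet the SLEDAI-2K and PGA criteria. A response to steroids can then be credited to pioglitazone or to placebo.

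The overlap is not remote. Section 9.2 expects that some patients will need therapy changes over 8 months, and section 8.1.2 describes B-level disease as suitable for lower-dose steroids, among other treatments. The permitted rescue is therefore aimed at the kind of event the endpoint should count as failure.

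**Working it through.** The plan states no Aim 2 response rate, flare rate, power or effect size, so there is no figure to reproduce. Two things can be checked: the coverage of the flare criterion, and whether any planned analysis changes who is classed as improved.

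**Coverage of the BILAG criterion.** Inputs: a treatment period of 3 months, about 91 days (section 8: "They will be treated for 3 months with 45 mg daily pioglitazone or placebo"); a permitted range of 75 to 105 days (section 9.5.3); a look-back of 4 weeks, or 28 days (Appendix 3). Coverage = look-back / period length.

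- 91 days: 28/91 = 0.31, leaving 63 days (9 weeks) unseen
- 75 days: 28/75 = 0.37, leaving 47 days unseen
- 105 days: 28/105 = 0.27, leaving 77 days unseen

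The preceding 4 weeks on the form serve only as the comparison for the last 4.

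**The SLEDAI-2K look-back** is stated two ways: 30 days in section 8.1.2 (30/91 = 0.33) and 10 days on the form in Appendix 2A (10/91 = 0.11). SLEDAI-2K and PGA are read here as end-of-period measures, so the 31% is a statement about the BILAG criterion only.

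**Does any analysis in section 11 reclassify a rescued patient?**

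- Regression or propensity adjustment for medications: adjusts the comparison for something that may arise after randomization; the responder status stays the same.
- Analysis of daily and cumulative prednisone: separate from the endpoint.
- Post hoc steroid adjustment: SLEDAI-2K only, and only for steroids beyond the permitted amount.
- Analysis of each component separately: uses the same end-of-period scores.
- Case-by-case review of medication changes by the investigator: can drop a patient from the analysis, but sets no rescue rule.

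None does.

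**Illustration of size; every rate is assumed.** Let f be the proportion of periods with an early, rescued flare and m the proportion of those that still meet all criteria at month 3 or 8. If rescue ought to count as failure, a responder rate is overstated by f × m.

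- f = 20% placebo, 10% pioglitazone, m = 60%: overstated by 12 and 6 points; the difference shrinks by (0.20 − 0.10) × 0.60 = 6 points
- f = 10% and 5%, m = 60%: the difference shrinks by (0.10 − 0.05) × 0.60 = 3 points
- f = 10% placebo, 20% pioglitazone, m = 60%: (0.10 − 0.20) × 0.60 = −6 points, so the difference moves 6 points in favour of pioglitazone

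For the effect on power, assume 25% success without rescue on placebo and 45% on pioglitazone, 75 observations per condition treated as unpaired, two-sided 0.05, and f = 20% and 10%.

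| m | placebo | pioglitazone | difference | power |
|---|---|---|---|---|
| 0 | 25% | 45% | 20 points | 0.73 |
| 25% | 30% | 47.5% | 17.5 points | 0.60 |
| 50% | 35% | 50% | 15 points | 0.46 |
| 75% | 40% | 52.5% | 12.5 points | 0.33 |

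The trial is a crossover, so the unpaired power figures show only the direction and rough scale of the loss.

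**The case against.** The strongest reply is that the endpoint may be an end-of-period assessment by design. In section 8.1.2 the phrase about the observation period describes other trials. Scoring status at month 3 or 8 whatever permitted rescue was given is a recognised treatment-policy choice and fits the intent-to-treat statement in section 11. This stands as a legitimate estimand, but the plan does not say it has chosen it. If flares over the whole period are meant, the schedule cannot deliver them. Either way the window and the role of rescue need stating.

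A reader might also infer stronger things that the documents do not support:

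- *That no early flare can reach the endpoint.* The BILAG form records items as improving, same, worse or new, so a flare still active in the last 4 weeks can be scored. Only one that resolves earlier is lost.
- *That every rescued patient is scored as improved.* The 20% SLEDAI-2K improvement and a significant PGA improvement are still required.
- *That the plan ignores steroids.* This is true of the responder definition, not of section 11 as a whole.
- *That a true benefit is necessarily diluted.* This needs more rescue on placebo; more on pioglitazone reverses the direction.
- *That harm would be hidden.* Adverse events are reviewed at months 1 and 6 and at unscheduled visits, lupus flare has its own definition in section 12.3.7, and the monitoring committee receives adverse events and concomitant medications and sees unblinded data (sections 11.2 and 12.5). Safety review of flares is separate and unaffected.

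**Conclusion.** The gap holds in limited form. As written and scheduled, the flare criterion covers about 31% of a treatment period (27% to 37%), and a patient whose early flare resolves on permitted prednisone can be classed as improved. This follows from the visit table, the BILAG look-back and the absence of a rescue rule. The window itself is inferred from those sources, because section 11 does not state one.

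The effect on the treatment comparison cannot be sized from the documents. The shifts of 3 to 6 points and the power losses shown rest entirely on assumed rates and on the view that rescue should count as failure. The direction is not fixed. Aim 2 is a secondary endpoint in a proof-of-concept trial, so this should be corrected but does not threaten the primary analysis.

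**What to change.** 1. In Table 3, schedule BILAG 2004 and SLEDAI-2K at unscheduled visits made for flare. In section 11, state that an A or B flare found at any visit within a treatment period makes that period not improved.
2. Prespecify an Aim 2 analysis, as the main definition or at least as a named sensitivity analysis, in which a patient-period is not improved if prednisone or an immunosuppressant was raised above its dose at the start of that period, for lupus activity, before the month 3 or month 8 visit. Medication changes are already asked about at study visits; the reason for each change must be recorded with them.
3. Do not use flare adverse events as a failure criterion yet. Section 12.3.7 calls a SLEDAI-2K rise of 3 or more a flare, while section 12.3.8.1 grades a rise of 2 to 4 as mild and gives no grade to a rise of exactly 9. These must be reconciled first, as must the 30-day and 10-day SLEDAI-2K look-backs.

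The cost is a few sentences in section 11 and activity scoring at visits that already include an examination. Responder rates will be somewhat lower. Flares managed away from the study site will still be seen only through medication records, and months 1 and 6 remain unscored. Nothing here changes what care is permitted.
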